 - Secondary objectives will be to compare group change in UUI episodes at 6 & 12 months, other voiding diary parameters (urinary frequency, pad counts, cure and "durable cure"), and change in the OAB-qSF and other questionnaires (see 1.2) at 2, 6 & 12 months.
- 2. Both a cross sectional study and RCT which will compare pre-treatment brain function in subjects with UUI to controls and compare the effect of hypnotherapy and pharmacotherapy on brain function in patients with UUI.
 - Up to eighty women (of the planned 152) with UUI will be recruited in order to obtain up to sixty analyzable fMRI datasets. Up to 30-35 normative controls will be recruited in order to achieve 25-30 analyzable fMRI datasets from normative controls. fMRI datasets from UUI patients will be compared to fMRI datasets from normative controls. The normative controls will be involved in the study for a month or less.
 - In addition, the same, up to 80, UUI subjects will also undergo fMRI analysis after receiving treatment (hypnotherapy or pharmacotherapy) for two months. Post treatment fMRI results from UUI subjects will be compared to their baseline images. These UUI subjects will complete the fMRI portion of the trial after being "on study" for 2 months but will continue to have follow up for the RCT analysis for one year (See #1 above)
 - Measured outcomes will be differences in baseline brain activation and connectivity in UUI subjects compared to controls as well as differences in treatment effect on brain activation and connectivity in subjects receiving pharmacotherapy compared to those receiving hypnotherapy

1. Study Objectives

1.1 Primary Objective:

- 1.1.1. To determine whether a mind/body therapy (hypnotherapy) is at least as effective and durable in treating urgency urinary incontinence (UUI) as a non-mind/body treatment (pharmacotherapy), comparing between group changes in UUI episodes recorded on voiding diaries at 2 months based on a non-inferiority design.
- 1.1.2. To determine whether hypnotherapy treatment of UUI (urgency urinary incontinence) is associated with greater modification of brain activation and connectivity on functional MRI than that which occurs following pharmacotherapy

1.2 Secondary Objectives:

- 1.2.1 To determine whether a mind/body therapy (hypnotherapy) is at least as effective and durable, in treating urgency urinary incontinence (UUI) as a non-mind/body treatment (pharmacotherapy).

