- 3. Between group differences in the post-treatment expectation question and between group differences in questionnaire change scores (the OAB-qSF, ISI, PISQ-12, Global questionnaire, CRADI-8, IBS Module, IC questionnaire) for Specific Aim 1 at 2, 6 and 12 month follow-up
- 4. Baseline differences in activation of the limbic cortex and brain connectivity in women with UUI compared to normative controls for Specific Aim 2

Overview:

Women with UUI who meet inclusion criteria and who choose to participate in the study will be enrolled at the University of New Mexico Urogynecology Clinic. We will screen subjects for study entry as we always do clinically, based on voiding diaries to ensure that subjects have UUI (and not other types of incontinence) and with a screening questionnaire, the OAB Awareness tool. Subjects will be randomized to treatment with either: 1) Pharmacotherapy (a standard therapy for UUI) and conventional behavioral therapy or 2) Hypnotherapy and conventional behavioral therapy. All subjects will give signed informed consent prior to study treatment. Approximately 152 women will be randomized to hypnotherapy or to pharmacotherapy with approximately half in each group. UUI subjects will be informed that study participation will be approximately 1 year; Measurements will be performed prior to treatment, following completion of treatment visits (treatment visits are performed over 8 weeks), and again at 6 and 12 months. The latter visits at 6 and 12 months do not necessarily require in-person

study visits and may be performed via phone and mail. The primary analysis of the RCT will be performed as an intention to treat analysis. A secondary analysis will be performed as a per protocol analysis.

A subset of subjects with UUI (up to 80) in both treatment groups will have brain fMRIs performed at baseline and follow-up at the Mind Research Network. In addition, 30-35 normative controls will also undergo an fMRI at the Mind Research Network to compare fMRI in affected women versus controls. Subjects will give signed informed consent prior to study participation

Randomization to treatment for RCT:

A. Randomization to treatment

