Visit 3 for fMRI subjects: Up to eighty of the UUI subjects (approximately half from the hypnotherapy group and half from the pharmacotherapy group) willing to have an fMRI and without contraindications to fMRI will participate in the fMRI portion of the study and will return for their baseline fMRI. Urine dipstick testing and pregnancy testing (in women who are premenopausal and without a history of a hysterectomy or permanent sterilization) will be performed: subjects who are pregnant or who have a urinary tract infection may not undergo fMRI testing. FMRI subjects will be pretreated with prophylactic antibiotics, will have a bladder catheter placed and will be asked to a) concentrate on a picture placed before them while they have the MRI performed b) they will next have their bladders filled with sterile fluid and be asked to rate the degree of bladder discomfort or "urge to void" experienced during bladder filling c) they will then have the catheters removed, the amount of urine voided will be measured and subjects will be discharged to home and given instructions to contact the study personnel if questions or problems arise.

The subjects will be randomized to treatment interventions and contacted by the study personnel and arrangements made for their interventions, which must begin within one month. Subjects will be administered the Patient Expectation question.

Visits Overview: Hypnotherapy subjects will have a total of 8 hypnotherapy sessions scheduled over 8 weeks and Conventional pharmacotherapy subjects will have a total of 8 visits scheduled over 8 weeks with the medication counselor (see the following)

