The principal purpose of this analysis will be to explore the mechanism of action of hypnotherapy when used to treat UUI, using pharmacotherapy as a control treatment that is not expected to exert its therapeutic effect via the brain. In addition we will explore the utilization of evoked activity and functional connectivity as biomarkers by correlating changes in these fMRI parameters with physiologic outcome measures, specifically UUI episodes. We understand that there is currently insufficient literature to determine the optimal method of assessing this correlation in the setting of a non-inferiority study design, and will look towards OCRA guidance on this aspect of the analytic plan in the future.

Treatment Assignment Procedures

Randomization to treatment

Study participants will be randomized to either pharmacotherapy or hypnotherapy groups using a computergenerated randomization scheme in varying permuted block sizes of 4-8. SAS 9.3[®] Proc-Plan software will create a randomization scheme of varying permuted block sizes of 4-8 to avoid severe inequality of group sizes for this 2 arm study. Subjects will be stratified based on fMRI performance and UUI severity (< 4 UUI episodes vs. \geq 4 UUI episodes on 3 day voiding diaries). UUI severity should be comparable in both groups because it is a potential risk factor for treatment failure. UUI severity will be defined by UUI frequency. Burgio⁸³ identified risk factors for unsuccessful behavioral treatment of UUI. Women with > 10 UUI episodes on baseline voiding diaries were much less likely to be completely continent after behavioral treatment. For purposes of this study, on a 3 day diary approximately 4 UUI episodes would be a potential risk factor for treatment failure and stratification will be performed in order to avoid UUI severity imbalances between the treatment groups. FMRI stratification will be performed to ensure appropriate representation of both treatment groups in the fMRI study.

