Statistical Analysis 2.2 Pre- and Post-Treatment measurements in patients with UUI: Efficacy of hypnotherapy and pharmacotherapy on anterior cingulate cortex and right insula activation will be compared using a 2x2 (Group x Time) mixed model ANCOVA to correct for potential differences in group characteristics (e.g. age). Analysis of treatment effect will be focused on the anterior cingulate cortex and insula based on preliminary data that suggests the effect size for change in activation will be highest in these regions. Prior functional MRI analysis during the hypnotic state has shown complete suppression of anterior cingulate cortex activation in response to pain.⁵⁵ However, the magnitude of suppression of anterior cingulate cortex or insula signal outside the hypnotic state has not been studied. Current study size will be able to detect differences between pre and post treatment signal within a treatment group with an effect size of approximately 0.5 and a power of 0.8. Minimal effect size would be approximately equivalent to a 60% decrease in the excess (above normative control) anterior cingulate cortex and insula signal. We predict a main effect of time, suggesting that both treatments are effective in reducing activity within the anterior cingulate cortex and insula. However, we also predict a significant Group x Time interaction, indicating that that change in activity will be greater for the hypnotherapy relative to the pharmacotherapy group. Minimum detectable effect size for the Group X Time interaction is 0.7 with power of 0.8 and alpha of 0.05. Simple effects tests will also be conducted to ensure that randomization to treatment arm was successful (i.e. no differences in baseline activity across the two groups).

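### A baseline significance test in the fMRI arms cannot show that randomization succeeded or that the arms are equal, and should be replaced by standardised differences plus adjustment for baseline signal

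*Combined protocol and SAP*

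**What the plan says.** Section 9.6, Statistical Analysis 2.2, compares the arms on anterior cingulate and right insula activation with a 2x2 Group x Time mixed model ANCOVA. Age is the only covariate named, as an example. The paragraph ends: "Simple effects tests will also be conducted to ensure that randomization to treatment arm was successful (i.e. no differences in baseline activity" (between the two arms). It gives no alpha, margin or interval for this test, and no action after either result. The next paragraph applies similar analyses to functional connectivity.

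On numbers, the Précis (Brief Description, item 2) states: "Up to eighty women (of the planned 152) with UUI will be recruited in order to obtain up to sixty analyzable fMRI datasets". Section 3 (Visit 3 for fMRI subjects) describes the scanned women as "approximately half from the hypnotherapy group and half from the pharmacotherapy group", and section 9.2 adds: "FMRI stratification will be performed to ensure appropriate representation of both treatment groups in the fMRI study". The baseline scan comes before randomization (section 3, Visit 3; Flow Diagram 1; section 6.2.2).

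The between-arm change in limbic activation and connectivity is listed as a primary outcome in sections 3, 9.1 and 9.51.

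**The concern.** The sentence treats a test result as evidence that two groups are the same, and that sameness as evidence that randomization worked. Neither step holds.

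- **A non-significant result does not show equality.** In a subset of this size the test leaves a wide range of true differences open.
- **A significant result does not show failed randomization.** Baseline signal is measured before allocation. If allocation was sound and all women are kept, any difference is chance by construction, and a larger sample would not change that.

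The one route to a real difference in the analysed set is loss of scans after randomization that is related to both signal and arm. The test cannot tell that apart from chance. At stake is a statement in the Aim 2 report that the arms were shown to be alike, or that randomization was unsuccessful, which the data could not support. A baseline imbalance would also carry into the Group x Time contrast through regression to the mean.

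**Working it through.** **Inputs.** Up to 60 analysable datasets from up to 80 women (Précis), split about evenly (section 3), so about 30 per arm, or 40 if every baseline scan is usable. Both are ceilings. Two-sided 0.05 is assumed: section 9.6 gives alpha 0.05 for the interaction and none for the baseline test. The 0.5-SD difference is an illustrative yardstick, not a figure from the plan.

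**1. The plan's own figures point to about 30 per arm.** It states: "Minimum detectable effect size for the Group X Time interaction is 0.7 with power of 0.8 and alpha of 0.05". At 30 per arm the normal approximation gives (1.960 + 0.842) × √(2/30) = 0.72, and the t distribution 0.74. Both round to 0.7; a strict 0.70 would need 33 per arm, a rounding-level gap. The second figure is a pre-post difference "within a treatment group with an effect size of approximately 0.5 and a power of 0.8"; at n = 30, 2.802/√30 = 0.51 (t: 0.53).

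**2. Largest imbalance that passes.** t(0.975, 58) × √(2/30) = 2.002 × 0.258 = 0.52 SD. Any observed difference up to that size is non-significant.

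**3. Miss rate for a true 0.5-SD difference.** The noncentrality is 0.5 × √(n/2).

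| Women per arm | Noncentrality | Power (t) | Missed |
|---|---|---|---|
| 25 | 1.77 | 0.410 | 59% |
| 30 | 1.94 | 0.478 | 52% |
| 40 | 2.24 | 0.598 | 40% |

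About 64 per arm would be needed for 80% power.

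**4. False alarms under sound randomization with no loss.** With independent tests at 0.05, two regions give 1 − 0.95² = 0.098. Adding one connectivity test gives 1 − 0.95³ = 0.143. Correlation between measures would lower these.

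**5. Effect on the Group x Time contrast.** Let D be the baseline imbalance in SD and ρ the test-retest correlation, with equal variances before and after. The spurious difference in change is (1 − ρ)D and the SD of change is √(2(1 − ρ)), so the shift in SD of change is D × √((1 − ρ)/2). Section 9.1 cites intra-class correlations frequently above 0.8, from other tasks.

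- ρ = 0.8: 0.5 × √0.10 = 0.158, which is 0.158/0.7 = 23% of the detectable effect.
- ρ = 0.9: 0.5 × √0.05 = 0.112, or 16%.

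This takes the plan's 0.7 to be in units of the SD of change, as step 1 suggests.

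**The case against.** The strongest reply is that nothing depends on the test. Section 9.6 attaches no threshold or action to it for Aim 2, and the Group x Time model is fitted whatever it shows. The provision to add covariates when baseline differences are found is written for Aim 1. That stands: a reader might infer that the Aim 2 analysis is gated on the test, and the documents do not say so. The stated purpose remains one the test cannot serve.

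Second, under sound allocation there is no true difference to detect, so a miss rate has no target unless scans are lost selectively. Even strong selection may not reach 0.5 SD. If one arm lost exactly its highest-signal quarter and the other lost a quarter at random, the mean would shift by 0.318/0.75 = 0.42 SD (normal signal assumed). A chance imbalance of 0.5 SD or more occurs only about 5% of the time at 30 per arm. This stands too, so 0.5 SD is illustrative only.

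Third, a reader might infer from 80 recruited and 60 analysable that a quarter of women drop out after randomization. The Précis does not say when datasets are lost. Pregnancy or urinary infection at Visit 3 can prevent a baseline scan before allocation, and section 10.3.3 allows for motion and artefact, which can spoil one. The image analysts are blinded to arm.

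Fourth, a reader might infer a larger bias by assuming poor repeatability: ρ = 0.5 would give 0.25 SD, or 36% of 0.7. The protocol's cited reliability does not support that as the main case, although its source is other tasks and treatment falls between the scans.

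**Conclusion.** The concern holds in a limited form. The planned test cannot establish what section 9.6 asks of it. At about 30 per arm it passes any observed imbalance up to 0.52 SD, and it would miss a true 0.5-SD difference 52% of the time (40% at 40 per arm). With sound allocation and full retention it would raise a false alarm in about 10% to 14% of trials.

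The likely distortion of the primary fMRI contrast is modest: about 0.16 SD of change or less, at most about 23% of the detectable effect, for an imbalance as large as 0.5 SD. These figures rest on two-sided 0.05, equal arms, independence between measures, equal variances over time, and ρ of about 0.8 or higher.

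The documents do not show that the arms will differ, that randomization is at risk, or how many scans are lost after allocation. This is a minor correction to the analysis text.

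**What to change.** In section 9.6, Statistical Analysis 2.2:

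1. Delete the sentence as a check of randomization.
2. Put in its place: *Baseline signal will be summarised by arm as a standardised difference with 95% CI, for all women with a usable baseline scan and for those in the Group x Time analysis. No test will be used to conclude that the arms are equal or that randomization succeeded or failed.* Setting the two groups of women side by side shows whether loss of scans has changed the balance. Women whose baseline scan is unusable cannot contribute.
3. Because a table does not correct regression to the mean, add: *The between-arm comparison of post-treatment signal (or change) will include baseline signal as a covariate, whatever imbalance is observed.* Apply the same to connectivity.

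The cost is one table from scans already collected and one covariate. Adjustment should not lose precision: residual variance relative to the change score is (1 − ρ²)/(2(1 − ρ)) = (1 + ρ)/2, or 0.90 at ρ = 0.8. The report can no longer state that there were no baseline differences. The intervals will also be wide, with a half-width of about 0.52 SD at 30 per arm and 0.45 SD at 40 (1.99 × √(2/40)). They exclude imbalance no better than the test did, but they show the uncertainty openly.

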10.1 Data Collection Forms

The Study Coordinator and her designee (neither of whom will perform data entry) will collect baseline information from subjects including Past medical history & Demographics sheet & baseline questionnaires (OAB-qSF, ISI, PBBC, PISQ-12, CRADI-8, IBS Module, BPIC, Expectation questionnaires administered) and 2, 6 and 12 month follow-up questionnaires and compliance information on CRFs. The questionnaires are standardized, validated questionnaires presented in their suggested paper formats. Unique patient identifiers are not included on the CRFs as the CRFs only include the research subject numbers, date and HRPO study # and CRF version numbers. The research staff responsible for data entry into the database will be blinded to subject randomization. The research nurse performing Cystometrics and fMRI tasks will not be involved in the fMRI interpretation. Drs. [name] and [name], who will perform fMRI interpretation, will be blinded to subject randomization.

During this study all medical history, physical exam information, testing results and questionnaires obtained at baseline and follow-up will be for research purposes only and data will be kept in strict confidence and will be identified with a study code number unique to the subject without other patient identifiers. The database will be secured with password protection. The database will be built using the web-based platform, REDCap®, as recommended by the UNM CTSC. The study's data entry personnel will receive only coded information that is entered into the database under those identification numbers. Only coded information without unique patient identifiers will be entered into the study database. Only study personnel will have access to individually identifiable private information and data. Confidentiality will be maintained by keeping paper-based study subject folders for all enrolled subjects in a locked cabinet in the Urogynecology research area (this folder will include case report forms, laboratory reports, questionnaires, voiding diaries, intake forms). A separate log linking patient codes and unique patient identifiers will be kept on password protected computer available to study personnel.

10.2 Data Management

Data will be collected on CRFs approved by the UNMH HRPO including demographic and patient history forms, eligibility forms, questionnaires, Cystometrics and fMRI task data sheets, pharmacotherapy side effect and hypnotherapy practice logs, treatment compliance logs as well as forms related to AE tracking. These data will be maintained as noted above by the Investigators and Research personnel. The database used by the UNM Urogynecology research team will be password protected. The database will be built using the web-based platform, REDCap®, as recommended by the UNM CTSC. The study's data entry personnel will receive only coded information that is entered into the database under those identification numbers. Only coded information without unique patient identifiers will be entered into the study database. Only study personnel will have access to individually identifiable private information and data. Confidentiality will be maintained by keeping paper-based study subject folders for all enrolled subjects in a locked cabinet in the Urogynecology research area (this folder will include case report forms, laboratory reports, guestionnaires, voiding diaries, intake forms). Consents will be kept separate from these research folders and will be kept in a separate locked cabinet in the UNM Research Administrative area. A separate log linking patient codes and unique patient identifiers will be kept on password protected computer available only to study personnel. CRFs will include forms used to collect subject information including demographic, medical history forms, questionnaires, compliance forms, fMRI screening forms, inclusion and exclusion criteria forms as well as patient behavioral therapy instruction handouts.

Data collected at the Mind Research Network using standardized paper forms or digitally will only be identified with the study's unique identifier (ID) for the participant. The link between the name of the participant and the study ID will be kept confidential by the MRN on a secure portal. All data storage devices at the Mind Research Network are encrypted devices. Personally identifying information will not be stored in files on networked computers and paper forms. Such information will be kept in separate locked file cabinets. Electronic data are doubly protected against computer catastrophe. Data will be backed up daily. The backup system will be used only by a designated administrator, preventing accidental deletion even by project staff.

10.3 Quality Assurance

10.3.1 Training

Research Study Staff all complete training as required by the UNM (these include; Research University workshop for Human Research Protections Office submissions, Human Research Protections training certification, UNM Financial Conflicts of Interest training, UNM Health Sciences Center Culture of Compliance, UNM Health Sciences Center Code of Conduct and Compliance, HIPAA and Breach Notification, HIPAA Training, HIPAA and Accounting of Disclosure, Cash Management Trainings and Ethics training (Ethics: A Framework for Ethical Decision Making). In completing these training classes, research staff acknowledge the rules and regulations regarding human subjects protection, HIPAA regulations compliance, and all University-related policies and procedures governing research. These classes provide each coordinator with the tools to effectively and efficiently execute research protocols and maintain compliance with federal, state, and university regulations. In addition, the Research Information Specialist has completed the following training: Certified Clinical Research Coordinator (for certification), Essentials of Leadership', Patient Scheduling and the 2011 NIH Regional Grants Seminar. Each employee's training profile is reviewed annually with the Research Information Specialist to assure compliance with federal, state, and university regulatiots to assure compliance with federal, state, and university context of the secure compliance with federal, state, and university for the secure compliance with federal, state, and university for the secure compliance with federal, state, and university to assure compliance with federal, state, and university for the secure compliance with federal, state, and university for the secure compliance with federal, state, and university guidelines.

Training for the medication counselor(s) will include 2-3 one hour training sessions, similar to the amount of training given in our hypnotherapy pilot study. Acceptability of counselor performance will be checked with the pharmacotherapy counseling fidelity checklist used by research staff to audit random sessions. Training for the hypnotherapists will include three 1-2 hour training sessions. Acceptability of hypnotherapist performance will be checked with the hypnotherapy fidelity checklist used by research staff to audit random sessions.

